7.7.2. Coding of Therapies

All therapies are coded using WHO-DRUG. In the table(s), the generic term will be used. Multiple records of the same generic term for the same subject with the same categorization will be counted only once. The table will therefore present subjects, not occurrences.

7.7.3. Analysis

Table 14.1.3.17: Prior therapies: Frequency table

Frequency tabulation per treatment group (and overall) of the ATC classes and generic terms, of “prior” and “prior+concomitant” therapies only.

These are all the therapies that were used before the first intake of study medication.

Population: safety.

Table 14.1.3.18: Concomitant therapies up to Week 12: Frequency table

Frequency tabulation per treatment group (and overall) of the ATC classes and generic terms, selecting both “concomitant” (with a start date during the first study period, or a missing start date) and “prior+concomitant” (all of them) therapies.

These are all the therapies that were used during the first 12 weeks of the study, concomitantly to the study medication.

Population: safety.

Table 14.1.3.19: Concomitant therapies over the whole study period: Frequency table

Frequency tabulation per treatment group (and overall) of the ATC classes and generic terms, selecting “concomitant” and “prior+concomitant” therapies only.

These are all the therapies that were used during the study, concomitantly to the study medication.

Population: safety.

Table 14.1.3.20: Post-treatment therapies over the whole study period: Frequency table

Frequency tabulation per treatment group (and overall) of the ATC classes and generic terms, selecting “post-treatment” therapies only.

These are all the therapies that were used during the study, but started after the last dose of study medication.

Population: safety.

Listing 16.2.4.5: Prior and concomitant therapies

Listing per treatment group and per subject of all data on prior and concomitant therapies. Flags for prior/concomitant/post-treatment will be added. In case the therapy was due to an AE, the AE preferred term will be mentioned in this listing.

Population: safety.

7.8. EXPOSURE TO STUDY MEDICATION AND COMPLIANCE

7.8.1. Derivations for placebo/GLPG0634

For the first period of the study (baseline – Week 12):

- Total treatment duration (days) = (last dose administration date – first dose administration date) + 1 day, where the last dose administration date is cut off on the day prior to the Week 12 visit. (“Prior to the Week 12 visit”, because at the Week 12 visit the re-randomization takes place and it is not known when exactly on that day the new study drug is being taken.)

- Total treatment duration, excluding days off drug (days): sum of all durations (last – first +1) in the drug log pages where there is a morning and/or evening dose >0 capsules, and where the last duration is cut off on the day prior to the Week 12 visit.
- Percentage days with an intake = $100\% \times \left(\frac{\text{total treatment duration, excluding days off drug}}{\text{total duration}} \right)$
- Total compliant treatment duration (days): sum of all durations (last – first +1) in the drug log pages where there is a morning and/or evening dose with exactly 2 capsules, and where the last duration is cut off on the day prior to the Week 12 visit.
- Percentage compliance = $100\% \times \left(\frac{\text{total compliant treatment duration}}{\text{total duration}} \right)$

The “total duration” used as denominator in the above formulae equals: (date of Week 12 visit) – (date of first drug intake). This total duration is not including the Week 12 visit itself, just like the above derivations, because of the treatment switch happening at Week 12 making it uncertain which drug intakes actually happened at the day of the visit itself.

For the total 24 weeks study period:

- Total treatment duration (days) = (last dose administration date – first dose administration date) + 1 day.
- Total treatment duration, excluding days off drug (days): sum of all durations (last – first +1) in the drug log pages where there is a morning and/or evening dose >0 capsules.
- Percentage days with an intake = $100\% \times \left(\frac{\text{total treatment duration, excluding days off drug}}{\text{total duration}} \right)$
- Total compliant treatment duration (days): sum of all durations (last – first +1) in the drug log pages where there is a morning and/or evening dose with exactly 2 capsules.
- Percentage compliance = $100\% \times \left(\frac{\text{total compliant treatment duration}}{\text{total duration}} \right)$

7.8.2. Tables up to Week 12

Table 14.1.4.1: Use of study medication up to Week 12: Descriptive statistics

Descriptive statistics per treatment group (and overall) of the total treatment duration (days) and the overall compliance (%).

Frequency tabulation per treatment group (and overall) of the two treatment duration parameters, categorized in weeks.

Frequency tabulation per treatment group (and overall) of the days with intake and compliance, categorized as:

<80% ;
 [80%,100%[;
 100% ;
]100%,120%] ;
 >120%.

Population: safety.

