#### **8.5 Investigational Products**

##### **8.5.1 Investigational Products Administered**

The study medication will consist of 25, 50 and 100 mg capsules of GLPG0634 for oral administration or matching placebo.

The following doses will be evaluated:

- GLPG0634 50 mg q.d.: 2 capsules of 25 mg GLPG0634 in the morning.
- GLPG0634 100 mg q.d.: 2 capsules of 50 mg GLPG0634 in the morning.
- GLPG0634 200 mg q.d.: 2 capsules of 100 mg GLPG0634 in the morning.
- Placebo: 2 placebo capsules in the morning.

At Week 12, all subjects on placebo and the subjects on the 50 mg dose who have not achieved a 20% improvement in SJC66 and TJC68 will be assigned (automatically via IXRS) to 100 mg q.d. in a blinded fashion and will continue the study until Week 24. Subjects in the other groups will maintain their randomized treatment until Week 24.

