#### **8.5.9 Treatment Compliance and Drug Accountability**

For each dose taken, the date, the time of intake, and the number of capsules taken should be recorded on the subject diary card.

The investigator or designated study personnel will maintain a log of all drug dispensed and returned. Drug supplies for each subject will be inventoried and accounted for throughout the study.

Subjects with a poor compliance (<80% or >120%) will be retained by the study site. If study drug compliance remains <80% or >120% between study visits, or if the subject missed more than 2 visits, the subject will be evaluated for potential discontinuation. Any discontinuation should be done in consultation with the Medical Monitor.

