#### **8.6.2.5 Week 12 (Visit 7)**

The Week 12 visit (Visit 7) will take place on Day 85 ± 2 calendar days relative to the start of study medication intake.

- Any remaining study medication as well as empty study medication containers will be returned to the investigator, and an accountability check will be performed.
- Any AEs that have occurred since signing the ICF will be documented and any changes in concomitant medication will be reported.
- Vital signs will be measured.
- A 12-lead ECG will be performed.
- A physical examination will be performed.
- The subject diary card will be collected, a summary will be recorded in the eCRF, and a new subject diary card will be dispensed.
- Blood samples for measurement of PK and PD parameters will be collected.
- Serum CRP will be measured.
- SJC66 and TJC68 evaluations will be performed.
- Physician's and Patient's Global Assessments of Disease Activity will be completed.
- The subject will complete the HAQ-DI.
- The subject will complete the FACIT fatigue scale and SF-36 questionnaire.
- Hematology, clinical chemistry, and urinalysis (dipstick and microscopy) tests will be performed on samples collected at this visit. A urine pregnancy test will be performed on females of childbearing potential.

At Visit 7, all subjects on placebo and the subjects on the 50 mg dose who have not achieved a 20% improvement in SJC66 and TJC68 will be assigned (automatically via IXRS) to 100 mg q.d. in a blinded fashion and will continue the study until Week 24. Subjects in the other groups will maintain their randomized treatment until Week 24.

When all of these procedures have been performed, the study medication will be dispensed according to the information provided using IXRS and the date of the next visit will be confirmed.

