#### **8.8.1.1 Datasets or Populations Analyzed**

All randomized subjects who received at least one dose of study medication and have at least one post-Baseline efficacy assessment will be included in the efficacy analysis (intent-to-treat [ITT]).

A secondary per-protocol analysis will be performed to confirm the ITT analysis, excluding subjects with major protocol deviations (such as Baseline CRP within normal range, Baseline TJC68 <8, Baseline SJC66 <6, <80% study medication compliance, or use of forbidden concomitant medications). Full details of the major protocol deviations will be described in the statistical analysis plan, with adherence to analysis sets agreed upon prior to database lock and unblinding.

All randomized subjects who received at least one dose of study medication will be included in the safety analysis.

All randomized subjects who received at least one dose of GLPG0634 and who have at least one PK measurement will be included in the PK analysis.

Reasons for study termination will be tabulated.

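### SAP 7.8.1 compliance percentage cannot register over-dosing, contradicts the >100% classes of its own table, and lacks a denominator for early stoppers and for 24 weeks

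*SAP*

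**What the plan says.** **Regimen.** Protocol 8.5.1 gives 2 capsules once daily in the morning in every arm; for the lowest dose it reads "2 capsules of 25 mg GLPG0634 in the morning". No evening dose is planned.

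**Compliance formula.** SAP 7.8.1 sums drug-log days "where there is a morning and/or evening dose with exactly 2 capsules" and divides by a total duration. A companion measure, percentage of days with an intake, counts days "where there is a morning and/or evening dose >0 capsules". In period 1 both numerators stop the day before the Week 12 visit, and the denominator is "date of Week 12 visit) – (date of first drug intake". The 24-week block repeats both percentages and again divides by a total duration, but does not define it.

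**Table.** For Table 14.1.4.1 (SAP 7.8.2) the specification reads "Frequency tabulation per treatment group (and overall) of the days with intake and compliance, categorized as": below 80%, 80% to below 100%, exactly 100%, above 100% up to 120%, and above 120%. Table 14.1.4.2 is to be similar for the whole study.

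**Uses of compliance elsewhere.** Protocol 8.5.9 asks for a subject to be evaluated for discontinuation "If study drug compliance remains <80% or >120% between study visits". Protocol 8.8.1.1 lists, among the major deviations that remove a subject from the per-protocol set, "<80% study medication compliance, or use of forbidden concomitant medications". It says the SAP will give full details of major deviations. SAP 7.2 refers instead to a Protocol Deviation Plan, and SAP 2.1.1 leaves the per-protocol set to a blind review meeting.

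**The concern.** A table with classes above 100% is meant to show subjects who took more than planned. The formula that feeds it counts days, and a day counts once or not at all, so extra capsules cannot raise the score. Depending on how they were taken, they either leave it unchanged or lower it. In a dose-finding trial the exposure table would then report no over-exposure by construction, and some over-dosed subjects would appear in the low-compliance class.

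The denominator is a second gap. It needs a Week 12 visit date, which a subject who stops earlier may not have, and nothing replaces it for 24 weeks. The programmer would have to choose, and the choice changes the result.

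**Working it through.** The documents state no compliance figure to reproduce, so the check applies the SAP rule to defined dosing patterns.

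**Inputs**
- Planned intake: 2 capsules per day, morning only (Protocol 8.5.1).
- Week 12 timing (Protocol 8.6.2.5): "The Week 12 visit (Visit 7) will take place on Day 85 ± 2 calendar days relative to the start of study medication intake".
- First intake is Day 1 (SAP 3.1), so the period 1 denominator is 85 − 1 = 84 days, or 82 to 86 over the visit window.
- Comparator: capsules taken / (2 × 84 = 168). This is an assumption made for the check; the documents define no such ratio.

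**Ceiling in period 1.** Dosing days run from Day 1 to the day before the visit. With drug-log records that do not overlap, the maximum is 82/82, 84/84 or 86/86 for a visit on Day 83, 85 or 87, which is 100% each time. The same ceiling holds for days with an intake. Neither measure can enter the two classes above 100%.

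**Patterns over 84 days**

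| Pattern (2 in the morning on other days) | SAP 7.8.1 | Capsule count |
|---|---|---|
| 2 morning + 2 evening, every day | 84/84 = 100% | 336/168 = 200% |
| 2 morning + 2 evening, 18 days | 84/84 = 100% | 204/168 = 121.4% |
| 4 in the morning, every day | 0/84 = 0% | 336/168 = 200% |
| 3 in the morning, 20 days | 64/84 = 76.2% | 188/168 = 111.9% |
| 4 in the morning, 17 days | 67/84 = 79.8% | 202/168 = 120.2% |
| 1 in the morning, 17 days | 67/84 = 79.8% | 151/168 = 89.9% |
| 1 morning + 1 evening, every day | 0/84 = 0% | 168/168 = 100% |
| none, 17 days | 67/84 = 79.8% | 134/168 = 79.8% |

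The two measures agree for wholly missed days. They part for extra capsules, in either direction, and also for partial or split doses. Falling below 80% takes at least 17 off-pattern days: 16 give 68/84 = 81.0%, 17 give 79.8%.

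**Early stoppers.** Take a subject who doses correctly for 42 days and then stops. Substituting the planned 84 days gives 42/84 = 50%; ending at the last dose gives 42/42 = 100%. The SAP does not choose.

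**24 weeks.** If the total duration is taken as last minus first dose plus one, the ceiling is again 100%. If it is taken as the Week 24 visit minus first intake, a dose on the Day 169 visit gives 169/168 = 100.6%, which comes from the day count and not from over-dosing. The >120% class is out of reach under both.

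**The case against.** **Counting correct-dose days is a legitimate measure of adherence.** This stands, and a capsule ratio has its own blind spot: no capsules on 17 days and 4 on another 17 gives 168/168 = 100% and hides 34 wrong-dose days. The subject with 3 capsules on 20 days was off the assigned dose on 20/84 = 23.8% of days, and leaving that subject out of a per-protocol set could be defended. The reason would be wrong dosing, though, not low compliance. None of this explains table classes that the chosen measure cannot fill.

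**The patterns are extreme.** They show the mechanism and say nothing about frequency, which the documents do not allow one to estimate. Protocol 8.5.4 describes kits that last until the next visit and mentions no overage, so doubling the dose every day would need about twice the supply.

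**Four stronger readings are tempting, and the documents do not support them.**
- *The per-protocol set is misclassified.* No text ties the 7.8.1 percentage to the <80% exclusion. The rule is left to the Protocol Deviation Plan, which is not among the documents, and to the blind review. The risk is conditional.
- *The protocol's >120% limit can never be met.* That limit is a site rule applied between visits, in a section built on diary cards and drug accountability. The SAP percentage neither implements nor blocks it.
- *A fully compliant subject scores about 200% at 24 weeks (168/84).* The SAP confines the Week 12 denominator to the formulas above it, in the period 1 block. The gap is a missing definition, not an instruction to reuse the wrong one.
- *Over-dosing is invisible.* Only the derived percentages and their tables miss it. Listing 16.2.5.1 shows the recorded study-medication data by subject.

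**Conclusion.** The concern holds as an internal contradiction and an incomplete definition. In period 1 the compliance percentage is capped at 100%, assuming non-overlapping log records, so the two upper classes of Table 14.1.4.1 will be empty regardless of what was taken. Extra capsules score as full compliance when taken as 2 + 2, and as non-compliance when 3 or more are taken at once (76.2% against 111.9% in the 20-day example). The denominator is missing for subjects without a Week 12 visit and for the 24-week period.

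The certain effect is on the exposure and compliance tables. An effect on the secondary per-protocol analysis follows only if this percentage is used for the <80% exclusion, which the documents do not state. In that case over-dosed subjects can be excluded as under-compliant, and so can subjects with partial doses on 17 or more of 84 days. Protocol 8.8.1.1 promised the details in the SAP, so the silence needs closing either way. The primary analysis, ACR20 at Week 12 in the ITT population with non-responder imputation, does not use compliance and is unaffected.

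**What to change.** In SAP 7.8.1:

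1. Define percentage compliance as 100 × capsules taken / capsules expected under the protocol regimen. Expected capsules run from first intake to the day before the Week 12 visit for period 1, and to the last dose date for early stoppers and for the 24-week period. Every arm takes 2 capsules daily, so the Week 12 switch does not change the expected count.
2. Keep the percentage of correct-dose days as a separate line in Tables 14.1.4.1 and 14.1.4.2, over the same stated periods, so that offsetting missed and extra doses remain visible.
3. State which measure applies the protocol's <80% per-protocol rule, and align the Protocol Deviation Plan with it.
4. Do not add a >120% per-protocol exclusion; Protocol 8.8.1.1 lists none.

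The cost is SAP wording and one more derivation. The present formula already reads capsule numbers from the drug-log pages, so no new data are needed. A few subjects may change compliance class, and the per-protocol set may change if the <80% rule draws on this figure. Both should be settled before database lock and unblinding.

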7.8.3. Tables for the whole 24 weeks period

Table 14.1.4.2: Use of study medication over the whole study period: Descriptive statistics

Similar to the preceding table, also using the 5 treatment sequences of Chapter 3.

7.8.4. Listings

Listing 16.2.5.1: Exposure to study medication: eCRF data

Listing per treatment group and per subject of all data related to the use of study medication as recorded in the eCRF.

Population: safety.

Listing 16.2.5.2: Exposure to study medication: Derived data

Listing per treatment group and per subject of all derived parameters related to the use of study medication.

Population: safety.

Listing 16.2.5.3: Dispensed kit numbers

Listing per treatment group and per subject of all dispensed placebo/GLPG0634 kit numbers, flagging any mistakes in dispensing.

Population: safety.

8. DEFINITIONS OF EFFICACY TABLES, LISTINGS AND FIGURES

Mock tables, listings and figures are provided in a separate document.

All analyses will be run on the ITT population, unless specified otherwise.

General comment on the efficacy data listings: listings will present the observed-case time points, with imputed data (for components) clearly flagged. The LOCF- or NRI-imputed time points will not be shown.

General comments on the observed-case analysis:

- Is done for efficacy tables and listings, but not for efficacy plots.
- Is done for all time points in the descriptive statistics.
- Is done for Week 12 only in the inferential statistics.
- Is done for ITT only; not for per-protocol.

8.1. ACR20, ACR50, ACR70 AND ACR-N**8.1.1. Parameters**

ACR20 response when:

- $\geq 20\%$ improvement from baseline in SJC66, and
- $\geq 20\%$ improvement from baseline in TJC68, and
- $\geq 20\%$ improvement from baseline in at least 3 of the following 5 items:
 - Pain VAS (taken from the HAQ-DI)
 - Patient's Global Assessment of Disease Activity VAS
 - Physician's Global Assessment of Disease Activity VAS
 - Total HAQ-DI score
 - CRP.

Subjects who do not meet this criterion are non-responders.

If any of the 7 components of the ACR20 would be missing, then this missing component will be imputed using the value of the last preceding nonmissing visit. If all components are missing, then the derived ACR20 will remain missing. Imputation of such cases for the tables will be done there using LOCF or NRI like any other missing value.

Subjects who discontinue within the first week so that ACR20/50/70 responses cannot be determined will be classified as non-responders.

The ACR50 and ACR70 responses are derived using the same algorithm, but with 50% and 70% cutoffs respectively.

Note that the primary endpoint of the study is the ACR20 at Week 12 in the ITT population, using NRI imputation.

The ACR-N is derived using the following formula:

ACR-N = MIN [% improvement in TJC68, % improvement in SJC66, MED % improvement in (patient's global assessment, physician's global assessment, patient's assessment of pain, HAQ-DI, CRP)]

So this is taking the smallest of the percentage increases in SJC66, TJC68, and the third of the remaining 5 parameters. In case the ACR-N is negative (i.e., the subject actually worsens instead of improves), then the ACR-N is replaced by a 0. The ACR-N is therefore a number between 0 and 100.

The ACR-N represents the percentage NN% according to which the subjects would have been an "ACRNN" responder.

(See further sections on how to derive these components.)

The time to ACR20 response

= (date of first time ACR20 response is reached) – (date of first medication intake) + 1 day, if the subject achieved ACR20 response during the initial 12 weeks treatment period, or
= MIN (date of the Week 12 visit, date of trial termination) – (date of first medication intake) + 1 day, in case the subject did not achieve ACR20 response at any time during the initial 12 weeks treatment period.

Next to this, the visit during which the ACR20 response was first recorded will be analyzed as well:

- Week 1
- Week 2
- Week 4
- Week 8
- Week 12
- Never (i.e., subject did not achieve ACR20 response during the initial 12 weeks of treatment).

The time to ACR50 response and the time to ACR70 response are defined in the same way.

Note that the study period 2 cannot be used for the time-to-event derivation, because of the predefined potential treatment shifts at Week 12.

Note that if for a specific visit both the regular CRP as well as the high-sensitive CRP are available, the high-sensitive CRP will be used for the derivation of the percentage change from baseline and also for the ACR20/50/70/N.

Note that the percentage change from baseline remains missing if the baseline value itself equals zero.

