4.4.2. Handling of missing values in scales or summary parameters

Missing items in scales or summary parameters will be imputed to allow for the derivation of the total scale/parameter score. The appropriate imputation rules will be described in the sections where the total scores are defined.

4.4.3. Handling of missing values and early dropouts in the efficacy analyses during the first study period (up to Week 12)

This is for the “efficacy chapter 2” analysis.

For binary data (e.g., ACR20), two different imputations will be done for missing visits as well as early dropouts: non-responder imputation (NRI) and LOCF, up to and including Week 12. The NRI imputation will be primary, and LOCF will be secondary.

For other data (ordinal or continuous), missing visits as well as early dropouts will be imputed using the last observation carried forward (LOCF) algorithm, up to and including Week 12.

Definitions of the imputation methods:

- LOCF (all types of parameters, from binary to continuous): to impute a missing value, the last preceding nonmissing value will be used (which could even be a baseline value).
- NRI (binary response parameters only): to impute a missing response, the subject will be assumed to be a non-responder.

For all parameters, an observed-case analysis will also be performed (i.e., without any imputation). The observed-case analysis will serve as a sensitivity analysis (to ascertain the impact of early dropouts on the results) and will basically be limited to:

- ACR20/50/70/N: descriptive at W12+W24 and inferential at W12
- EULAR remission: descriptive at W12+W24
- SDAI/CDAI: descriptive at BSL+W12+W24
- DAS28: descriptive at BSL+W12+W24 and inferential at W12
- All ACR components (VAS, joint counts, CRP, HAQ-DI): descriptive at BSL+W12+W24
- QoL (FACIT,SF-36): descriptive at BSL+W12+W24.

4.4.4. Handling of missing values and early dropouts in the efficacy analyses during the study period as a whole (full 24 weeks)

This is for the “efficacy chapter 2” analysis.

For binary data (e.g., ACR20), two different imputations will be done for missing visits as well as early dropouts: non-responder imputation (NRI) and LOCF, up to and including Week 24. The NRI imputation will be primary, and LOCF will be secondary.

For other data (ordinal or continuous), missing visits as well as early dropouts will be imputed using the last observation carried forward (LOCF) algorithm, up to and including Week 24.

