6.1.2. Efficacy Variables

6.1.2.1. Definition of primary efficacy endpoint: ACR20 at Week 12

The primary endpoint is the percentage of subjects achieving an ACR20 response at Week 12. Other time points will be regarded as secondary endpoints. The non-responder imputation (NRI) of the ACR20 will be the primary parameter, with observed-case and last observation carried forward (LOCF) imputation as secondary confirmatory analyses.

The ACR response is a measurement of improvement in multiple disease assessment criteria. The ACR20 response is defined as:

≥20% improvement from baseline in SJC66 (66 joints) and TJC68 (68 joints)

AND

≥20% improvement from baseline in at least 3 of the following 5 assessments

- Pain (VAS) in cm (from HAQ-DI).
- Patient's Global Assessment of Disease Activity (VAS) in cm.
- Physician's Global Assessment of Disease Activity (VAS) in cm.
- Patient's Assessment of Physical Function as measured by HAQ-DI.
- CRP in mg/L.

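### One stray component in the Week 12 window is enough to switch off non-responder imputation: carried-forward joint counts can then make a dropout a Week 12 ACR20 responder in the primary analysis

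*SAP*

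**What the plan says.** SAP 6.1.2.1 fixes the primary analysis: "The non-responder imputation (NRI) of the ACR20 will be the primary parameter". SAP 8.1.1 repeats it: "Note that the primary endpoint of the study is the ACR20 at Week 12 in the ITT population, using NRI imputation". SAP 4.4.3 defines NRI as a rule about the response: "to impute a missing response, the subject will be assumed to be a non-responder".

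Whether a response counts as missing is decided earlier, in the derivation in SAP 8.1.1. If any of the seven components is missing, "then this missing component will be imputed using the value of the last preceding nonmissing visit". The section continues: "If all components are missing, then the derived ACR20 will remain missing". Only those cases reach the visit-level step: "Imputation of such cases for the tables will be done there using LOCF or NRI like any other missing value".

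The SAP sets no minimum number of observed components, does not require an observed joint count, and does not limit how old a carried value may be.

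Three other provisions decide what can fall in the Week 12 window:
- SAP 3.3 assigns visits, including early discontinuation and unscheduled ones, to windows by study day. Week 12 is Day 71 to 98. Follow-up visits have no window.
- SAP 3.4 selects data separately for each parameter when several are measured.
- Protocol 8.7.1.4.2 places CRP in the clinical chemistry panel.

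**The concern.** NRI is usually chosen so that a subject without the Week 12 assessment does not count as a success. Here that protection is lost once any one of the seven components has a value in the window. CRP is the likeliest to appear alone, because it can come from a blood draw with no clinical assessment.

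A dropout's status in the primary analysis can then depend on an incidental sample rather than on the state of the joints at Week 12. Protocol 8.3.4 requires an unscheduled retest within 3 to 5 days of learning of a listed laboratory abnormality. It also asks for repeated creatinine tests after discontinuation in some subjects. If such abnormalities are related to dose, the extra samples could be unevenly spread across arms. The documents do not show that this happens.

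At stake is a possible small bias in the Week 12 ACR20 rates, which also feed the interim analysis supporting phase III dose selection.

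**Working it through.** **1. The plan's own figure.** Protocol 8.8.2 has n = 70 per arm, alpha = 5%/3 and a chi-square method. The two-sided form without continuity correction is

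power = Φ{[(p1 − p0) − z(1−α/2)·√(2·p̄·(1−p̄)/n)] / √[(p0(1−p0) + p1(1−p1))/n]}, where p̄ is the mean of p0 and p1.

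| Placebo vs active | Stated power | Recomputed |
|---|---|---|
| 15% vs 43% | 90% | 90.7% |
| 40% vs 70% | 90% | 89.1% |
| 15% vs 39% | 80% | 79.8% |
| 40% vs 67% | 80% | 80.0% |

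The design figures reproduce. They are used below only as a scale.

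**2. Two subjects under the rule.** Both meet ACR20 at Week 8 and discontinue with a full early discontinuation visit on Day 68. That day falls in the Week 8 window, Day 43 to 70.

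| | Subject A | Subject B |
|---|---|---|
| Data on Day 71 to 98 | none | unscheduled chemistry sample including CRP, e.g. Day 72 |
| Components observed at Week 12 | 0 of 7 | 1 of 7 |
| Derived ACR20 | missing | derived from 1 observed and 6 carried values |
| Primary (NRI) result | non-responder | responder, if the carried values meet the criteria |

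Their clinical information is the same. Only the blood sample differs.

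**3. What one observed component must show.** Code each component as improved by at least 20% or not, giving 2^7 = 128 patterns. A responder needs both joint counts and at least three of the other five: C(5,3) + C(5,4) + C(5,5) = 10 + 5 + 1 = 16 patterns.
- If the sole observed item is one of the five non-joint items and it has **not** improved, the subject can still respond on both carried joint counts and at least three of the other four items: C(4,3) + C(4,4) = 4 + 1 = 5 patterns.
- If the sole observed item is a joint count, that count must itself have improved.
- A carried baseline value is a 0% change and cannot count as improvement. The route therefore needs an earlier post-baseline response in the carried components.

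**4. Size.** One subject changes an arm's rate by 1/70 = 1.4 points. With k_a such subjects in an active arm and k_p on placebo, the difference changes by (k_a − k_p)/70: 1.4 points for one against none, and zero for one against one. The design differences are 28 to 30 points for 90% power and 24 to 27 for 80%.

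**5. Possible cost of a stricter rule.** Assume that the design rates include responders who depend on carried components, and that a share f of the active arm is reset to non-responder. The values of f are assumptions; the documents give none.

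| f (subjects of 70) | 43% vs 15%: active arm only | both arms, same proportion | 70% vs 40%: active arm only | both arms, same proportion |
|---|---|---|---|---|
| 0% (0) | 90.7% | 90.7% | 89.1% | 89.1% |
| 1% (0.7) | 88.5% | 89.5% | 86.4% | 87.9% |
| 3% (2.1) | 83.1% | 87.0% | 80.0% | 85.4% |
| 5% (3.5) | 76.2% | 84.1% | 72.1% | 82.6% |

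In the proportional columns, placebo loses the same fraction of its responders as the active arm. The table shows what the fix might cost, not harm from the current rule.

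**The case against.** **It is a prespecified two-level scheme.** SAP 4.4.2 treats gaps inside a summary measure as a separate matter: "Missing items in scales or summary parameters will be imputed to allow for the derivation of the total scale/parameter score". SAP 4.4.3 then ranks NRI over LOCF for missing visits and early dropouts. A reader might infer that carrying components forward breaks the SAP's own ranking. It does not, because that ranking is not about components. This stands: the SAP is not contradicting itself, and the point concerns how far the component rule reaches.

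**The SAP promises nothing about conservatism.** A reader might infer that it claims a conservative property for NRI and then fails to deliver it. The SAP only defines NRI and makes it primary. Its worst-case wording in section 2.4.1 concerns as-randomized and as-treated grouping.

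**The single-component case is rare.** The Week 12 and early discontinuation visits collect CRP, both joint counts, both global assessments and the HAQ-DI with its pain scale together. An early discontinuation visit on Day 71 to 98 therefore normally supplies the full set. The Follow-up visit has chemistry without joint counts, but it is not windowed. What remains is mainly an unscheduled sample in that span, in a subject with no full assessment there. The retest rule does not say that CRP is included. This also stands.

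**Imputed components will be flagged.** SAP section 8 flags them in the listings, so affected subjects can be found. That does not measure their effect on the primary result. Nor does the observed-case analysis clearly do so. SAP 4.4.3 describes it as free of imputation, but SAP 8.1.1 gives only one ACR20 derivation and the observed-case listings contain imputed components.

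**Conclusion.** The point holds. As written, one component in the Day 71 to 98 window keeps a subject out of NRI, so the primary analysis can count a Week 12 responder with no Week 12 joint count. No other section overrides this, and no planned ACR20 table uses a different derivation.

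The effect is probably small. Each subject is worth 1.4 points in one arm, and less in the difference from placebo if arms are affected alike. Against a planned difference of 24 to 30 points, a few such subjects would not reverse a large effect. They could matter for a dose near the multiplicity-adjusted threshold or in the between-dose comparisons.

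A reader might go further and put a rate on it, for example a few percent of each arm with partial Week 12 data. The documents support no such figure. It would also mix in subjects with one lost CRP result or one blank scale, whose joint counts were observed. An imbalance between arms is likewise possible but not shown. The reason to act is that the rule lets a dropout's status turn on an incidental blood sample, and that closing the gap is cheap.

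**What to change.** In SAP 8.1.1, add a rule for the NRI analysis of ACR20, ACR50 and ACR70. A subject is a responder only if SJC66 and TJC68 are both observed in the visit window and meet the threshold, and at least three of the other five components are observed in the window and meet it. Otherwise the subject is a non-responder. Keep component carry-forward for the LOCF analysis. Report by arm how many Week 12 responders depend on carried components.

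At minimum, run this as a Week 12 sensitivity analysis beside the present derivation. SAP 6.3.2 already lists changes made after the interim lock, so a change to the primary derivation at this stage would need to be recorded there as post-interim.

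The cost is one paragraph and one derivation flag. A subject with an isolated gap stays a responder if both joint counts and three improved items were observed. A subject who needs a carried item to reach three does not. Response rates may therefore fall slightly, and power with them, by an amount that depends on the unknown share affected.
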